8.1.8.1 Timing of Dose Administration

Lenvatinib capsules are to be taken orally once daily at approximately the same time without regard to food intake from C1D1 onwards. Participants should not take lenvatinib on PK sampling days prior to their appointment (ie, C1D1, C1D15, and C2D1). On C1D1, C1D15 and C2D1, participants should be instructed to bring their lenvatinib to the clinic. Lenvatinib should be administered at the study site at approximately the same time of day to accommodate PK sample collection timing.

If a participant misses a dose, it may be taken within 12 hours after the usual time of the dose. If more than 12 hours have elapsed from the time of the usual daily dose, lenvatinib should be taken the next day at the usual time. In the event a participant vomits after lenvatinib administration, the participant should not take another dose until the next scheduled dose.

8.1.8.2 Compliance

Lenvatinib compliance will be calculated by the Sponsor based on the study drug accountability documented by the site staff and monitored by the Sponsor/designee. The objective is 100% compliance and investigators and their staff should evaluate compliance at each visit and take appropriate steps to optimize compliance.

8.1.9 Discontinuation and Withdrawal

Participants who discontinue study intervention prior to completion of the treatment period should be encouraged to continue to be followed for all remaining study visits as outlined in the SoA.

Participants who withdraw from the study should be encouraged to complete all applicable activities scheduled for the EOT visit at the time of withdrawal. Any AEs that are present at the time of withdrawal should be followed in accordance with the safety requirements outlined in Section 8.4.

8.1.10 Participant Blinding/Unblinding

This is an open-label study; there is no blinding for this study.

8.1.11 Calibration of Equipment

The investigator or qualified designee has the responsibility to ensure that any device or instrument used for a clinical evaluation/test during a clinical study that provides information about inclusion/exclusion criteria and/or safety or anti-tumor activity parameters shall be suitably calibrated and/or maintained to ensure that the data obtained are reliable and/or reproducible. Documentation of equipment calibration must be retained as source documentation at the study site.

8.1.12 Demography

Participant demography information will be collected at the Screening Visit. Demography information includes date of birth (or age), sex, and race/ethnicity (recorded in accordance with prevailing regulations). Tanner staging will be collected at the Screening Visit or C1D1, at EOT, and during efficacy and survival FU. During efficacy and survival FU, perform annually until puberty has completed or through survival FU, whichever comes first. Telephone contact is acceptable for assessment if clinic visits are not possible at post-treatment visits after the 30-day safety FU.

8.2 Efficacy/Immunogenicity Assessments

8.2.1 Tumor Imaging and Assessment of Disease

In addition to survival, evaluation of antitumor activity will be assessed based on imaging evaluation of changes in tumor burden over time, until the participant is discontinued from the study or goes into survival follow-up. The process for image collection can be found in the SIM.

For participants with non-CNS solid tumors:

- CT scans of the chest, abdomen and pelvis are required.
- As an alternative to CT (i.e., when iodinated contrast is contraindicated or when mandated by local practice), MRI of the abdomen and pelvis, along with a noncontrast CT of the chest is an acceptable alternative.
- If brain imaging is performed to document the stability of existing metastases, MRI should be used if possible. If MRI is medically contraindicated, CT with contrast is an acceptable alternative.
- Any additional anatomical areas as clinically indicated.

For participants with CNS Tumors:

- MRI of the brain is required for the HGG cohort. MRI of the brain is strongly preferred over CT for non-HGG CNS tumors.
- Any additional anatomical areas as clinically indicated.

Tumor imaging will be performed at the timepoints specified in Section 1.3, or as clinically indicated. Tumor imaging of the chest is to be acquired by CT scan. For the abdomen and pelvis, contrast-enhanced MRI may be used when CT with iodinated contrast is contraindicated, or when mandated by local practice. **MRI is the strongly preferred modality for imaging the brain. For HGG participants, MRI is mandatory to allow for RANO assessment.** Refer to the SIM for mandatory acquisition parameters. The same imaging technique should be used in a participant throughout the study to optimize the reproducibility of the assessment of existing and new tumor burden and improve the accuracy of the response assessment based on imaging. Note: for the purposes of assessing tumor imaging, the term “investigator” refers to the local investigator at the site and/or the radiological reviewer at the site or at an offsite facility.

8.2.1.1 Initial Tumor Imaging

Initial tumor imaging at Screening must be performed within 28 days prior to the date of allocation. Tumor imaging performed as part of routine clinical management is acceptable for use as screening tumor imaging if it is of diagnostic quality and performed within 28 days prior to the date of allocation.

Participant eligibility will be determined based on confirmation by the investigator that the participant has measurable disease per RECIST 1.1 for all tumor types except for HGG, which will be evaluated per RANO criteria. In addition, participants with neuroblastoma who do not have measurable disease per RECIST 1.1 but have MIBG-positive evaluable disease may be enrolled (see Section 4.2.1.1).

8.2.1.2 Tumor Imaging During the Study

The first on-study imaging assessment should be performed the end of Week 8 \pm 7 days. Subsequent tumor imaging should be performed every 8 weeks until Week 24, then every 12 weeks (\pm 7days) thereafter during treatment (or sooner if there is evidence of PD). Imaging timing should follow calendar days from C1D1, and should not be adjusted for delays in cycle starts. Imaging should continue to be performed until disease progression is identified by the investigator, the start of new anticancer treatment, pregnancy, withdrawal of consent, or death, whichever occurs first.

Objective response should be confirmed by a repeat imaging assessment. Tumor imaging to confirm PR or CR should be performed at least 4 weeks after the first indication of a response is observed. Participants will then return to regular scheduled imaging, starting with the next scheduled imaging time point. Participants who receive additional imaging for confirmation do not need to undergo the next scheduled tumor imaging if it is less than 4 weeks later; tumor imaging may resume at the subsequent scheduled imaging time point.

8.2.1.3 End-of-Treatment and Follow-up Tumor Imaging

For participants who discontinue study intervention, tumor imaging should be performed at the time of treatment discontinuation (\pm 4 week window). If previous imaging was obtained within 4 weeks prior to the date of discontinuation, then imaging at treatment discontinuation is not mandatory. For participants who discontinue study intervention due to documented disease progression, this is the final required tumor imaging.

For participants who discontinue study intervention without documented disease progression, every effort should be made to continue monitoring disease status by tumor imaging using the same imaging schedule used while on treatment calculated from the date of allocation until the start of a new anticancer treatment, disease progression, pregnancy, death, withdrawal of consent, or the end of the study, whichever occurs first.

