5.5 Participant Replacement Strategy

A participant who is not evaluable for objective response will be replaced.

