9.5 Analysis Populations

9.5.1 Efficacy Analysis Population

The EAS population will serve as the primary population for the analysis of antitumor activity data within each tumor type in this study. EAS is defined as all evaluable participants, who have measurable disease present at baseline and at least 1 postbaseline efficacy assessment, unless they have discontinued prior to the first efficacy assessment due to progressive disease. Details on the approach to handling missing data are provided in [Table 5](#).

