9.6 Statistical Methods

9.6.1 Statistical Methods for Efficacy Analyses

This section describes the statistical methods that address the primary and secondary efficacy objectives. Methods related to exploratory objectives will be described in the sSAP.

Antitumor activity data will be analyzed by each tumor type. The data cutoff for the primary study analysis for a given tumor type will be determined by the study team, based on the review of data at each interim analysis and predetermined futility guidance.

Only those participants who have measurable disease present at baseline and have their disease re-evaluated at postbaseline visits will be considered evaluable for ORR. These participants will have their response classified according to RECIST 1.1 or RANO for participants with HGG.

Primary Efficacy Analysis

ORR: Objective responses will count only confirmed CR and PR at Week 16. Estimated ORR and its exact 95% CI using the method of Clopper and Pearson will be presented.

Secondary Efficacy Analyses

The BOR will be provided with the descriptive statistics. The ORR, DCR, and CBR will be provided with exact 95% CIs using the method of Clopper and Pearson, and the DOR will be analyzed for responders using Kaplan-Meier approach.

The secondary endpoint of PFS will be analyzed using Kaplan-Meier product-limit estimates. Median PFS and the cumulative probability of PFS at 4, 6, 12, and 24 months will be presented with 2-sided, 95% CIs when an adequate number of at-risk participants at those time points warrant the estimate. The cumulative PFS probabilities will be plotted over time as appropriate.

A summary of the primary analysis strategy for the key efficacy endpoints is provided in [Table 5](#).

Table 5 Table Analysis Strategy for Key Efficacy Variables

Endpoint/Variable	Statistical Method	Analysis Population	Missing Data Approach
Primary Analyses – Within tumor type			
ORR (RECIST 1.1 or RANO for HGG) at Week 16	Summary statistics using Clopper and Pearson method	EAS	Participants in EAS with missing data are considered nonresponders.
Secondary Analyses – Within tumor type			
ORR	Summary statistics using Clopper and Pearson method	EAS	Participants in EAS with missing data are considered nonresponders.
BOR	Summary statistics using Clopper and Pearson method	EAS	Missing observation in EAS population are counted as nonresponders.

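### The end-of-treatment scan can be waived on the strength of the screening scan, so a few early stoppers without progression can be left with no postbaseline assessment and be replaced (minor)

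*Combined protocol and SAP*

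**What the plan says.** Section 8.2.1.3 sets out an end-of-treatment scan and then a waiver. For those who discontinue, "tumor imaging should be performed at the time of treatment discontinuation", with a window of 4 weeks either side. The waiver follows: "If previous imaging was obtained within 4 weeks prior to the date of discontinuation, then imaging at treatment discontinuation is not mandatory".

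Four other provisions determine what the waiver does:

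- Section 8.2.1.1, baseline imaging: "Initial tumor imaging at Screening must be performed within 28 days prior to the date of allocation".
- Section 8.2.1.2, first scheduled postbaseline imaging: "The first on-study imaging assessment should be performed the end of Week 8", plus or minus 7 days.
- Section 9.5.1, membership of the EAS: measurable disease at baseline and "at least 1 postbaseline efficacy assessment, unless they have discontinued prior to the first efficacy assessment due to progressive disease".
- Section 5.5, replacement: "A participant who is not evaluable for objective response will be replaced".

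Table 5 (Section 9.6.1) treats missing data as nonresponse, but only for participants already in the EAS. Section 4.1 bases the futility rule on no response among the first 9 evaluable participants.

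**The concern.** A scan taken before the first dose cannot show what happened after it. Yet for someone who stops very early, the screening scan will usually be the only earlier imaging, and as worded it is enough to make the end-of-treatment scan optional. That scan is often the only postbaseline assessment such a participant would have before Week 8.

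Without it, and without a later follow-up scan, a participant who stopped for toxicity, by choice, or for lack of benefit in the investigator's opinion has no postbaseline assessment. Section 7.1 lists that last reason separately from objective progression. The participant is then outside the EAS, beyond the reach of the missing-as-nonresponder rule, and is replaced by someone else. Had the participant been assessed, the result would almost always be nonresponse: a response needs confirmation at least 4 weeks later, and SD needs at least 7 weeks from first dose. The loss is therefore one-directional for ORR, DCR and CBR, and it also affects who fills the first 9 evaluable places.

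**Working it through.** The plan states no figure for this. Its design assumptions and interim boundaries are redacted, so there is nothing to reproduce. The check is date arithmetic followed by an illustration.

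**When the screening scan meets the waiver.** Let s be the days from screening scan to C1D1 (1 to 28, Table 1 and Section 8.2.1.1) and t the days from C1D1 to discontinuation. The waiver is met by the screening scan when s + t ≤ 28, that is, t ≤ 28 − s.

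| Scan before C1D1 (s) | Stops covered (t) |
|---|---|
| 1 day | up to 27 days |
| 7 days | up to 21 days |
| 14 days | up to 14 days |
| 21 days | up to 7 days |
| 28 days | only on C1D1 itself |

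Assume s is uniform on 1 to 28 and t uniform on 0 to 27. Then 406 of 28 × 28 = 784 pairs qualify, or 52%. Counting the stop day from 1 to 28 instead gives 378/784 = 48%. So about half of stops in the first 4 weeks are covered.

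**From an early stop to a lost participant.** Let p be the share of treated participants who stop in the first 4 weeks without recorded progression. The documents do not give p; 5% to 15% is assumed. Let m be the share of those under the waiver who end with no postbaseline scan, also assumed. The chance of at least one loss among 9 treated is 1 − (1 − 0.518 p m)^9.

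| Event among 9 treated | p = 5% | p = 15% |
|---|---|---|
| Any such early stop, 1 − (1 − p)^9 | 37% | 77% |
| Any early stop under the waiver (m = 1) | 21% | 52% |
| Any lost, if half end unscanned (m = 0.5) | 11% | 30% |
| Any lost, if a quarter end unscanned (m = 0.25) | 6% | 16% |

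With 48% in place of 52%, the last three rows become 20% to 49%, 10% to 28% and 5% to 15%.

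**Effect on ORR.** One replaced nonresponder moves 1/10 = 10.0% to 1/9 = 11.1%. Two replaced nonresponders move 3/19 = 15.8% to 3/17 = 17.6%. The exact 95% intervals are far wider: 0.3% to 48% for 1/9 and 3.8% to 43% for 3/17.

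**Effect on the futility rule.** With a response rate of 10% among evaluable participants (assumed), the chance of at least 1 response in 9 is 1 − 0.9^9 = 61.3%. If a share f of entrants were such stoppers and were counted as nonresponders, it would be 1 − (1 − 0.1(1 − f))^9:

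- f = 0.518 × 0.15 × 0.5 = 3.9%: 59.7%.
- f = 0.518 × 0.15 = 7.8% (nobody under the waiver is ever scanned): 58.1%.

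Under these assumptions the waiver adds at most about 3 percentage points to the chance of passing.

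**PFS.** Table 5 censors PFS at the last assessment. An extra scan showing PD adds an event; one showing no PD adds only a short censored time. The affected group stopped without recorded progression, so the balance between the two is unknown.

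**The case against.** The strongest reply is that the plan already covers most of these participants, and much of it stands.

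- **Progression stops are kept.** Under Section 9.5.1, someone who stops before the first assessment because of progressive disease stays in the EAS.
- **Imaging continues after stopping.** Sections 1.1, 4.1, 8.2.1.3 and 8.11.5.2 call for continued scans when treatment stops without progression, so a Week 8 scan is still expected and would make the participant evaluable. The duty is best-effort, however, and ends at new anticancer therapy, death, pregnancy or withdrawal of consent.
- **New therapy may count as progression.** Section 6.5.1 treats additional anticancer therapy as evidence of progression. But it is written for therapy given during screening and treatment. It does not say that a participant who stopped for toxicity and switched later discontinued because of progression.
- **The waiver is not the main cause.** The end-of-treatment scan is a recommendation, and the waiver does not forbid it. Exclusion and replacement come from Sections 9.5.1 and 5.5.
- **Other text may already settle it.** The tumor-imaging row of Table 1 could not be checked here, and the Site Imaging Manual is a separate document. Either might define qualifying imaging.

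A reader might infer that everyone who stops in the first 4 weeks is dropped and replaced, or that the 37% to 77% above is the chance of losing someone. The documents support neither. The waiver reaches only stops within 28 days of the screening scan, progression stops remain, and those who have a later scan remain. A reader might also infer that PFS is inflated; the censoring rule does not show that.

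What survives is narrow: the wording lets a baseline scan stand in for a postbaseline one, and nothing else in the sections available guarantees that the gap is filled.

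**Conclusion.** The gap in the wording is real and its consequence is minor. Losing a participant through it requires four things together: a stop within 28 days of the screening scan, a reason other than progressive disease, no end-of-treatment scan, and departure from imaging follow-up before Week 8. Where that happens, a near-certain nonresponder leaves the EAS and is replaced, which favours higher ORR, DCR and CBR and passing the futility rule.

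The likely size is one participant in a cohort, or none. That is about 1 percentage point on ORR at n = 9 and, under the assumptions above, at most about 3 points on passing futility. These figures rest on uniform timing, a 5% to 15% early-stop share and an assumed share left unscanned, none of which the documents give. For PFS, no direction can be claimed.

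The practical reach is now mainly the RMS cohort. Sections 1.1 and 4.4 record that the EWS and HGG cohorts were not expanded and that enrollment into the other solid tumors cohort was discontinued.

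**What to change.** Reword the waiver in Section 8.2.1.3, and in the imaging manual if it repeats the rule, along these lines: *the scan at discontinuation may be omitted only if a scan performed after C1D1 falls in the preceding 4 weeks; the screening scan does not count for this purpose.* Do not tie the scan to the start of any new anticancer treatment; its timing can stay within the existing window.

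Some early stoppers will still miss the scan, so add a sensitivity analysis of ORR, DCR and CBR. It should include all treated participants with measurable disease at baseline and count those without a postbaseline scan as nonresponders. This also addresses the larger contribution of the EAS and replacement rules.

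In the same edit, bring Section 9.6.1 into line with Section 9.5.1. The former says "Only those participants who have measurable disease present at baseline and have their disease re-evaluated at postbaseline visits will be considered evaluable for ORR" and omits the exception for progression before the first assessment.

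The cost is a sentence or two of text and one extra table per cohort. The real downside is that a few early stoppers would have the planned scan soon after their baseline one; for non-CNS tumors this means imaging of chest, abdomen and pelvis, in a mainly pediatric population.

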8.2.1.4 RECIST 1.1 Assessment of Disease

RECIST 1.1 will be used as the primary measure for assessment of tumor response (except for HGG), for date of disease progression, and as a basis for all protocol guidelines related to disease status (eg, discontinuation of study intervention). RECIST 1.1 references a maximum of 5 target lesions in total and 2 per organ.

8.2.1.5 RANO Assessment of Disease

RANO criteria will be used for participants with HGG as the primary measure for assessment of tumor response for date of disease progression, and as a basis for all protocol guidelines related to disease status (eg, discontinuation of study intervention). A standard MRI-imaging protocol will be performed for use in the assessments. Refer to Appendix 8 for RANO response criteria.

8.2.2 Palatability and Acceptability of Lenvatinib Suspension Formulation

The palatability and acceptability of lenvatinib suspension formulation will be assessed using a palatability questionnaire. All participants who receive suspension formulation, with the exception of participants using a NG or G tube, must complete the questionnaire according to the SoA. If the participant is unable to complete the questionnaire, this must be done by a parent or legal guardian. Measurement of palatability will be assessed using a facial hedonic scale [Guinard, J. X. 2001].

8.3 Safety Assessments

Details regarding specific safety procedures/assessments to be performed in this study are provided. The total amount of blood/tissue to be drawn/collected over the course of the study (from prestudy to poststudy visits), including approximate blood/tissue volumes drawn/collected by visit and by sample type per participant, can be found in the laboratory manual. Refer to Appendix 7 for country-specific requirements.

Planned time points for all safety assessments are provided in the SoA.

8.3.1 Physical Examinations

A comprehensive physical and oral examination or symptom-directed physical and oral examination will be performed as designated in the SoA (Section 1.3). A complete physical and oral examination at C1D1 will be performed only if the screening physical and oral examination was performed >7 days prior to C1D1.

A comprehensive physical and oral examination will include evaluations of the head, eyes, ears, nose, mouth including maxillary and mandibular mucosa, throat, neck, chest (including heart and lungs), abdomen, limbs, and skin, and a complete neurological examination. A urogenital examination will only be required in the presence of clinical symptoms related to this region.

Investigators should pay special attention to clinical signs related to previous serious illnesses.

8.3.2 Dental Examination

Information from studies in animals suggest that there is a risk of delayed tooth formation and/or physical growth and development. Therefore, dental examinations are being performed to evaluate participants for potential anomalies in tooth formation and eruption schedule.

Dental examination by a dentist or qualified dental professional should be conducted per local institutional guidelines during screening and thereafter per local standard of care, but no less than annually, and at EOT. The baseline dental examination can occur up to 4 weeks after the first dose of study intervention. If the most recent dental examination is within 6 months prior to the EOT visit, the dental examination is not required.

Post-screening dental examinations are not required for participants for whom permanent teeth (excluding third molars) are evaluated to be fully erupted at screening.

